### **9.1.3. Target Population and Study Samples**

**i. Target Population.** The proposed trial design calls for the enrollment patients with ICH  $\geq 30$  mL and not requiring extraventricular drainage (EVD) for the management of obstructive hydrocephalus. The proposed plan includes patients with ICH clots in all locations of the brain.

**ii. Intent-to-Treat Sample.** As the primary analysis, all efficacy and safety outcome measures are analyzed under the ITT. Under this principle, the evaluable sample includes all subjects who are randomized and receive at least one dose of Alteplase and each subject is analyzed according to the treatment group to which they were assigned at the time of randomization.

**iii. Safety Analysis Sample.** All randomized subjects are included in the safety analysis sample.

**iv. Per-Protocol Sample.** The potential for cross-overs in this study is minimal; none occurred in the phase II trial. However, in the case of cross-overs, a per-protocol sample will be constructed and examined in which treatment-as-received is analyzed. Given that clot resolution is a potentially treatment-related post-randomization variable, this covariate will be examined as an important potential mediator of final outcomes as part of a per-protocol analysis.

**9.1.4. Overall Methodology Description.** Statistical analyses will be performed on data that have been quality-assured through the Data Coordinating Center's (DCC)

protocols and monitoring reviews and have been exported by the DCC directly from the MISTIE III data base (Section D.3.e - DCC grant). The following analysis procedures may be applied to blinded (no treatment arm designation, for study investigators and staff), partially unblinded (treatment designation only as A and B, for DSMB and at interim analyses), and unblinded (full treatment designation, for final analyses) data, by DCC staff having the appropriate role permissions.

**9.1.5. Patient Disposition.** Summary statistics will be presented for the analysis sets and subgroups, the patients who completed the study, the patients who discontinued early from the study, and the reasons for early discontinuation including bleeding, loss to follow up, patient withdrawal or refusal, other complicating disease, error, or other reasons.

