After placement of the catheter and a CT scan to confirm correct placement, a six-hour post-surgical stabilization period is required prior to first injection of rt-PA. Keep the drainage system to drainage for six hours post catheter placement *prior* to first dose of rt-PA. This time is mandated to reduce the possibility of secondary hemorrhage. If new bleeding or bleeding expansion is seen on the post-op CT scan, wait 12 hours and repeat the CT scan. When the bleeding is stable, dosing can be initiated.

If post-operative clot volume is 10 to 15 mL, rt-PA should not be given. The catheter should remain in place and open to drainage for 24-36 hours prior to removal.

**Catheter adjustment/replacement:** Correct catheter placement will be CT-confirmed locally and post-operative measurements will be repeated centrally by the Surgical Center. Catheter adjustments will be made at this time, if necessary. If the hematoma appears larger or the shape is altered on CT scan after the catheter is placed, the catheter may require repositioning and a post-repositioning CT scan to confirm correct placement within the clot as well as stability of clot size. Repositioning is defined as the partial removal or “pull back” of the non-optimally placed catheter. Replacement is defined as removal of the catheter and replacement with a better targeted catheter using the introducer method described above with either the same or a different trajectory of insertion. There is a one-time allowance for a new rigid cannula placement. Soft catheter placements or replacements, usually done through an existing burr hole and always done using a stylet with image guidance, do not count against this limited number of rigid cannula passes. There is no limit to the number of soft catheter placements or replacements as long as stability requirements are met. Occasionally it may be necessary to create a new burr hole/trajectory to access the clot. This will be done only after consultation with the Surgical Center. Repeat CT scan and upload DICOMs of the final catheter placement in the clot into the EDC for Surgical

Center review and approval of catheter location in residual hematoma prior to dosing.

The catheter is then tunneled subcutaneously, connected using sterile technique to a three-way stopcock and then to a closed drainage system. Level the drainage bag to zero.

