If the catheter must be repositioned or replaced after dosing has begun, the procedure must be done equal to or greater than 24 hours after the most recent dose and all stability protocols must be repeated as if this were the original catheter placement.

Complete replacement of the catheter is allowed if the catheter to clot relation has been disturbed by inadvertent catheter movement or partial clot reduction. Complete replacement should be performed only once (i.e., in any subject only two, new rigid cannulas may ever be placed).

If repositioning or replacement does not correct the catheter-clot relation and the rigid cannula has already been replaced once during the trial, rt-PA administration must be stopped or not initiated and the catheter removed 24 hours later. This requirement will control the delivery of rt-PA only into space containing clot that can be lysed. The catheter may be left in place greater than 24 hours later if the catheter supports ventricular drainage as clinically required.

In addition, an unscheduled CT scan must be performed should the subject clinically deteriorate or significantly improve his or her GCS score. These additional safety provisions will keep under surveillance the most ideal time for stopping drug after clot is fully lysed.

**Catheter removal.** After keeping the catheter closed for the one hour following the last dose of rt-PA, the catheter should be opened and then left open to drain for 24-36 hours prior to catheter removal. The catheter must be closed at the time of removal and not open to air to avoid pneumocephalus. The catheter may be left in place greater than 24 hours later if the catheter supports ventricular drainage as clinically required.

To limit infection risk, remove the catheter at the bedside 24 to 36 hours after the last rt-PA administration, unless the catheter supports ventricular drainage as clinically required. Send the catheter tip for culture. A CT scan must be done 24 hours post catheter removal and examined for stability, new bleeding, or hemorrhage extension.

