#### 5.4 Adherence Assessment

Protocol adherence will be determined by review of data recorded on the case report forms that has been verified through comparison with the medical record and other source documentation. Compliance and treatment fidelity will be reported overall and by center to the DSMB at each scheduled review session. Study centers demonstrating poor protocol compliance will be retrained and, if necessary, replaced.

6 CLINICAL AND LABORATORY EVALUATIONS6.1 Schedule of Evaluations

	Screening / Baseline	Day 1 (day of randomization)	Day 2	Day 3	Days* 4 - 6	Day 7	Day 30 ± 7 days	Day 90 ± 7 days	Day 180 ± 14 days	Day 270 ± 14 days	Day 365 ± 14 days
Diagnostic CT	X										
Informed consent	X										
Stability CT (6 hours after diagnostic CT)	X										
Pregnancy test	X										
Medical History/ Review of Systems	X										
CTA (MRA)/MRI	X					Day 7-10 ± 1 day X (MRI)					
Image-Guided Catheter Placement + Aspiration (Surgical Group Only)		X									
Post catheter placement CT scan		X									
rt-PA admin. (Surgical Group Only; Q8h up to 9 doses)		X	X	X							
MTI-M3 specimen collection		X	X	X	X						
Daily CT Scan		X§	X	X	X (Day 4)		X†		X†		
		obtain a CT 24 h post catheter removal on any of these days									
Vital Signs		X	X	X	X						
Neurocheck		X	X	X	X						
Lab Assessments*	X	X	X	X	X						
Concomitant treatments	X	X	X	X	X	X	X	X	X	X	X
NIHSS	X					X	X		X		X
Barthel Index	X						X	X	X	X	X
Modified Rankin Scale	Historic						X	X	X	X	X
Stroke Impact Scale							X		X		X
GOS-E Scale							X		X		X
Mini-Mental Exam							X		X		X
Euro-Quol-5D Scale							X	X	X	X	X
PBSI							X		X		X
Personal Health Utility Assessment Interview									X		
CES-D									X		

\*Assessments should be performed daily through Day 6 regardless of treatment assignment.

†An MRI is an acceptable substitute for this CT scan with Coordinating Center approval.

§Subjects enrolled to medical management: The Day 1 CT scan does not need to be repeated if enrollment occurs on the same calendar day as the stability CT scan (done 6h post the diagnostic CT scan).

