## 8 CRITERIA FOR INTERVENTION DISCONTINUATION

rt-PA administration will be discontinued for any of the following reasons:

1. Dosing will be discontinued when the ICH clot volume is reduced to less than or equal to 10 mL, or the subject receives 9 doses of rt-PA (treatment endpoint), whichever occurs first.
2. Dosing will not be started if the ICH clot volume is reduced to less than or equal to 10 mL by clot aspiration alone during catheter placement (surgical endpoint).
3. The subject experiences a clinically significant bleeding event (local or systemic) (treatment failure).
4. In the investigator’s judgment, withdrawal from the trial would be in the subject’s best interest (treatment failure).
5. The subject or legal representative withdraws consent.

All subjects will be followed by the site team through day 365 (reasons 1 to 5) as part of the outcome assessment for the intervention. The use of the phone and mail will be the main means of maintaining contact after discharge. The subject or legal representative has the right to withdraw consent. At the time of consent withdrawal, the site personnel will discuss with the subject or legal representative the level of their consent withdrawal to determine if they are willing to discontinue study treatment but agree to in-person and by phone follow up visits, disagree to follow up visits but agree to phone contact to determine vital status, or no further contact at all.

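### Protocol 9.1.3.ii makes a dose of Alteplase a condition of the ITT sample, although only the surgical arm can receive one

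*Protocol*

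**What the plan says.** Protocol 9.1.3.ii places the efficacy and safety outcomes under ITT and then restricts the set: "Under this principle, the evaluable sample includes all subjects who are randomized and receive at least one dose of Alteplase". The same sentence goes on to say that subjects are analysed in their randomized group. The next item, 9.1.3.iii, has no such restriction: "All randomized subjects are included in the safety analysis sample".

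The schedule in Protocol 6.1 shows who can meet the condition: "rt-PA admin. (Surgical Group Only; Q8h up to 9 doses". The Choice of Control paragraph in Protocol 2.1 says that controls get conventional medical treatment only, without vehicle or placebo.

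The protocol also creates surgical subjects who are never dosed:

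- Section 5.1.2 imposes a delay: "a six-hour post-surgical stabilization period is required prior to first injection of rt-PA".
- Section 5.1.2, where the catheter cannot be brought into a proper relation with the clot: "rt-PA administration must be stopped or not initiated and the catheter removed 24 hours later".
- Section 5.1.2, where little clot is left after surgery: "If post-operative clot volume is 10 to 15 mL, rt-PA should not be given".
- Section 8, on a similar situation: "Dosing will not be started if the ICH clot volume is reduced to less than or equal to 10 mL by clot aspiration alone".

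The volume wording of the last two differs, and those passages must be reconciled. Section 8 nevertheless keeps such subjects under observation: "All subjects will be followed by the site team through day 365 (reasons 1 to 5) as part of the outcome assessment".

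SAP 5.2 analyses each eligible subject in the arm assigned at randomization, gives a total of 500, and has no dose condition.

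**The concern.** An ITT set is meant to depend on nothing that happens after randomization. Here membership depends on receiving a drug that one arm never gets. The clause therefore either empties the control arm or acts as a filter on the surgical arm only.

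The filter is the more dangerous reading because it can be carried out. It drops two kinds of surgical subject, both linked to prognosis. Some do poorly early: they die or deteriorate before the first dose is allowed, or the catheter cannot be placed properly. Others do well early, because aspiration alone removed most of the clot. No matching controls are removed. In an open-label surgical trial this gives up the protection of randomization for the protocol's 180-day primary analysis. Having two ITT definitions also leaves room to choose the analysis set after results are known.

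**Working it through.** **1. The clause against the rest of the plan**

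| Place | What it requires | Fits the dose condition? |
|---|---|---|
| Protocol 9.1, Primary Efficacy | ITT, 250 randomized to each arm | Not on the literal reading |
| Protocol 9.1.7.a, equation (1) | Treatment indicator 0 for medically managed patients | Not on the literal reading: no controls remain |
| Protocol 9.1.7.a, after equation (4) | ITT effect of one assignment against the other | No, on either reading |
| Protocol 9.1.3.iii | Safety set is everyone randomized | No: 9.1.3.ii puts safety outcomes under the dosed set |
| SAP 5.2 | Analysis as assigned, no dose condition | No |
| SAP 11.1 | Predictions for every participant in both arms | No |

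**2. The plan's own power figures**

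Inputs from Protocol 9.1.9: 250 per arm; 25% against 38% (stated power 88%) and 20% against 31% (stated 81%); two-sided 5%. Power = Φ(d/SE − 1.96), with SE = √[p₀(1−p₀)/250 + p₁(1−p₁)/250].

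- 25% vs 38%: SE = 0.0411, d/SE = 0.13/0.0411 = 3.16, power 88.5%.
- 20% vs 31%: SE = 0.0387, d/SE = 0.11/0.0387 = 2.84, power 81.2%.

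A pooled-variance version gives 0.8811 and 0.8075. The group-sequential bounds in Protocol Table 1 give 0.8769 and 0.8011. The stated figures therefore reproduce with all 250 subjects per arm.

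**3. Literal reading**

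Evaluable controls treated as planned: 0 of 250. No comparison is possible.

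**4. Condition applied to the surgical arm only (illustration)**

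The documents give neither the undosed share u nor the good-outcome rate g among the undosed. Both are assumed here: u = 5% or 10%, g = 10% or 60%. With p the good-outcome rate in the full surgical arm, the rate among the dosed is (p − u·g)/(1 − u).

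*Shift in the surgical rate*, with p = 36% (25% medical plus 11 points):

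| u | g | Rate among dosed | Shift (points) |
|---|---|---|---|
| 5% | 10% | (0.36 − 0.005)/0.95 = 37.4% | +1.4 |
| 10% | 10% | (0.36 − 0.010)/0.90 = 38.9% | +2.9 |
| 5% | 60% | (0.36 − 0.030)/0.95 = 34.7% | −1.3 |
| 10% | 60% | (0.36 − 0.060)/0.90 = 33.3% | −2.7 |

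*Chance of a false win for surgery*, with 25% in both full arms, 250 controls, 250(1 − u) surgical subjects and an unadjusted, unpooled z-test. The last columns use a critical value of 1.96 and the final bound of 2.03 in Protocol Table 1.

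| u | g | Rate among dosed | P at 1.96 | P at 2.03 |
|---|---|---|---|---|
| 0 | – | 25.0% | 2.5% | 2.1% |
| 5% | 10% | 25.8% | 3.9% | 3.4% |
| 10% | 10% | 26.7% | 6.1% | 5.3% |
| 5% | 60% | 23.2% | 0.7% | 0.6% |
| 10% | 60% | 21.1% | 0.15% | 0.12% |

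Worked row, u = 10%, g = 10%: SE = √(0.2667·0.7333/225 + 0.25·0.75/250) = 0.0402; z shift = 0.0167/0.0402 = 0.414; P = 1 − Φ(1.96 − 0.414) = 6.1%.

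The loss of numbers alone matters much less. With 10% undosed and the effect unchanged, pooled-variance power is 86.4% and 78.7%.

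**The case against.** The best defence is that the SAP already deals with this. It is evidently the later document: it records the move of the primary outcome to 365 days and cites papers from 2016 and 2017. Its ITT definition has no dose condition, its primary estimator uses every participant, and it makes the 180-day mRS a secondary outcome (Secondary 5a) analysed by the same methods. The literal reading is also unworkable, so nobody could apply it unnoticed. The clause looks like a drafting leftover, as does the reference to EVD plus rt-PA in SAP 13.2.1.

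Much of this stands. If the SAP is followed, its primary estimator is unaffected. It does not settle the matter, because neither document says which prevails and the protocol still gives the wrong definition for its own primary analysis. The surgical-only reading remains open to anyone who finds the literal one impossible.

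Two narrower objections also have force. First, some passages count only against the literal reading: 250 randomized per arm is not the same as 250 analysed, and follow-up to day 365 concerns data collection rather than set membership. The clear contradictions are the assignment-based estimand, 9.1.3.iii and SAP 5.2. Second, the false-win figures rest on assumed extremes and a simple z-test, whereas the protocol specifies a covariate-standardized Wald test with group-sequential bounds. At 2.03 the inflated values are 3.4% and 5.3% against 2.1% without bias: smaller, but still inflated. Intermediate values of g would shrink the bias.

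**Conclusion.** The concern holds, and the clause must be corrected. That conclusion rests on the text alone: a dose condition that only one arm can meet is incompatible with ITT, with the protocol's stated estimand and with SAP 5.2.

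The size is certain only for the literal reading, which leaves no evaluable controls treated as planned. For the surgical-only reading, the shifts of +1.4 to +2.9 or −1.3 to −2.7 points, and false-win rates of 3.9% to 6.1% or below 1%, are sensitivity illustrations on assumed undosed shares and outcome rates. The true undosed group mixes early failures and early successes, so the direction of bias cannot be told in advance. The power calculation itself is sound. The defect lies in the protocol's definition, not in the SAP's primary estimator.

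**What to change.** In Protocol 9.1.3.ii, delete the requirement of at least one dose of Alteplase. Define ITT identically in both documents: all randomized subjects, analysed in the arm assigned, whether or not surgery was performed or drug given. Sets based on dosing or exposure should appear only as separately named as-treated or per-protocol analyses, for which Protocol 9.1.3.iv and SAP 5.4 already provide.

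Two clarifications in SAP 5.2 are worth making at the same time but are of lower priority. Delete or reword the sentence that links exposure to the MISTIE procedure with intention to treat. State that eligibility means eligibility confirmed before randomization, as SAP 6.0 describes, so that a subject found ineligible later stays in the set.

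The change is one clause in the protocol and two clarifying sentences in the SAP. It needs no new data and leaves sample size and stated power as they are. The real cost is administrative: Protocol 11.1 sends modifications to IRB or ethics review, and the synopsis plans about 90 to 100 centers, so the edit is best bundled with another amendment if one is due.

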**9.1.6. Baseline Characteristics.**

i. **Demographics.** Summary statistics will be presented for age (years), gender, ethnicity, presentation center, hypertension history, diabetes, coumadin use, antiplatelet drug use.

ii. **Medical History.** Summary statistics will be presented for medical history, as well as presentation temperature, pulse, systolic blood pressure, and diastolic blood pressure. Presenting NIHSS, intracranial pressure (ICP), ICH volume, IVH volume, location of bleed and IVH score will be provided.

**9.1.7. Efficacy Analyses**

**9.1.7.a.** Analysis by MISTIE III Specific Aims

Primary Aims

**Hypothesis 1a:** Minimally invasive surgery (MIS) plus recombinant tissue plasminogen activator (rt-PA) for 3 days for the treatment of ICH improves functional outcome at 180 days as measured by the adjudicated mRS 0-3 by an estimated 13% increase as compared to the medically-managed patients. The null hypothesis will be a test of no improvement of MIS+rt-PA over medical management. Below is a description of the procedure for computing estimators of the treatment difference in probability of mRS 0-3 at 180 days post-stroke, for the study's population.

**Analysis 1a:** To evaluate this null hypothesis in the context of the covariate-adaptive randomization scheme, the model in equation (1) will be used, where Trt is 1 for MIS+rt-PA patients and 0 for medically-managed patients, ICH is pre-randomization ICH clot volume, GCS, Age, Diabetes and CVD (cardiovascular disease) are at randomization.

$$(\text{logit}(\text{Prob}[mRS \leq 3])) = \beta_0 + \beta_1 \text{Trt} + \beta_2 \text{ICH} + \beta_3 \text{GCS} + \beta_4 \text{Age} + \beta_5 \text{Diabetes} + \beta_6 \text{CVD} \quad (1)$$

The standardized estimator of the marginal treatment effect, in the form of RD, will then be computed. The advantage of this estimator, compared to the estimator based on a simple test of proportions using a z-test without covariates, is that it can lead to greater power for hypothesis testing.

The estimator in this approach is standardized to the overall distribution of covariates in equation (1) across the two treatment arms. Under this framework, the probability of a good outcome is defined under two scenarios for each patient: if assigned to MIS+rt-PA treatment vs. if assigned to the standard medical treatment arm (i.e. the counter-factual probabilities). The counter-factual probabilities based on model 1 are presented below as equations (2) and (3):

$$\mu_{1i} = \text{logit}^{-1}(\hat{\beta}_0 + \hat{\beta}_1 + \hat{\beta}_2 ICH_i + \hat{\beta}_3 GCS_i + \hat{\beta}_4 Age_i + \hat{\beta}_5 Diabetes_i + \hat{\beta}_6 CVD_i) \quad (2)$$

$$\mu_{0i} = \text{logit}^{-1}(\hat{\beta}_0 + \hat{\beta}_2 ICH_i + \hat{\beta}_3 GCS_i + \hat{\beta}_4 Age_i + \hat{\beta}_5 Diabetes_i + \hat{\beta}_6 CVD_i) \quad (3)$$

In equation (2), all patients are ‘forced’ into the MIS+rt-PA group (i.e., Trt=1) and  $\hat{\beta}_1$  estimates the treatment effect, while in equation (3), all patients are ‘forced’ into medical management (i.e., Trt=0) and  $\hat{\beta}_1$  drops out. The standardized estimator of the average treatment effect, using (2) and (3) above, is obtained by first computing the average of the patient-specific counter-factual probabilities of a good outcome under assignment to each treatment arm, across all patients. Next the difference is taken between this average under assignment to the MIS+rt-PA arm, and this average under assignment to the medical management arm.

To derive the average treatment effect, the patient-specific probabilities are averaged across patients. The average treatment effect on the log odds ratio scale can be formulated according to equation (4).

$$RD = \frac{1}{n} (\sum_{i=1}^n \hat{\mu}_{1i} - \sum_{i=1}^n \hat{\mu}_{0i}) \quad (4)$$

It has been shown that this estimator is consistent even if the model in equation (1) is mis-specified. To test the null hypothesis, a Wald statistic will be computed that is equal to the above estimator of the ITT average treatment effect between assignment to MIS+rt-PA versus assignment to medical management (on the risk difference scale) divided by its estimated standard error. Rejection of this null hypothesis will be based on group sequential thresholds (Table 1 below).

In subsequent analyses the model in equation (1) will be modified to include another baseline severity measure, such as NIHSS. In addition, a model with IVH volume will be explored. The models will be compared using Akaike Information Criterion (AIC) to assess the best combinations of predictors. The discriminatory ability of the models will be compared using cross-validated area under the Receiver Operating Characteristic (ROC) curve.

**Hypothesis 1b:** Early use of MIS plus rt-PA for 3 days for the treatment of ICH is as safe as medically-managed ICH, as measured by rates of procedure-related mortality, rebleeding, and infection within 30 days post-randomization. The null hypothesis is: *Early use of MIS+rt-PA is worse than medical management for a specific safety measure.*

**Analyses 1b:** The number of severe adverse events (SAEs) will be tabulated by SAE type at each follow-up time point for the total population as well as by treatment group, with particular emphasis placed on group differences at 30 days post-randomization. Any treatment group differences in SAEs enumerated for interim analyses will remain blinded to investigators associated with this study. Partially un-blinded results (e.g. group ‘A’ versus ‘B’ where the labels ‘A’ and ‘B’ are randomly assigned to the surgical and medically-managed groups) will be made available only during the closed sessions of DSMB meetings.

Methods of equivalence will be used to statistically determine if the proportions of a particular type of SAE are equal among both treatment groups in order to test the hypothesis that MIS plus rt-PA is safe. Equivalence testing deems the rates of any event to be equivalent between populations as long as the group difference in this rate is statistically within some pre-specified tolerance. For this trial, the tolerance value will be defined as 10% for the primary adverse events of 30-day mortality, rebleeding, and infection, and 5% for first-week operative mortality. Thus, the rates of adverse events seen in the MIS+rt-PA group can be higher than those in the medically-managed group, and yet still be considered equivalent as long as the upper one-sided 95% confidence intervals on rate differences are  $\leq 10\%$ , or  $\leq 5\%$ , depending on the safety measure.

